UNIVERSITY of LIMERICK

OLLS COIL LUIMNIGH

Statistical Plan

An evaluation of a Milk-Based Nutritional Supplement to Effect a Positive Change in Bone Health in Post-Menopausal Women at Risk of Osteoporosis.

Research Question or hypothesis:

Ho: Compared to a placebo control, ingestion of a milk protein-based supplement will not affect the temporal acute (0-4h) and diurnal (24h) rates of bone turnover in post-menopausal women with osteopenia.

Brief Background: In a novel approach to the timing of nutrient ingestion, the proposed nutrient intervention seeks to modify (reduce) the rate of bone resorption and promote the rate of bone formation to the benefit of bone health in post-menopausal women aged 50 to 70y diagnosed with osteopenia.

Study Design: A block randomised, crossover design

Participants: 16 post-menopausal women aged 50 to 70y diagnosed with osteopenia.

[figure not shown]
Statistical Analysis: ANOVA(R)

Independent variables:

TIME [6]
 0, 1, 2 3 4 and 24h

TEST PRODUCT [2]
 Placebo, MBPS

MODEL: Mixed model analysis of variance

Dependent variables

Bone Turnover [3]
 Blood CTX (bone resorption)
 Blood N1PD (bone formation)
 Urine DPD/Creatinine (bone resorption)

- a. Within-subject factor, **TIME (6)**
- b. Within-subject factor, **TEST PRODUCT (2)**
- c. Bonferroni corrected post-hoc comparisons

- i. Violation to normality (Shapiro – Wilk) data will be transformed by rank for analysis
- ii. Violation to homogeneity of variance-covariance matrices (Mauchly's W), e correction factors (Green-House Geisser, Huynh-Feld) will be applied
- iii. Violation to homogeneity of variance for post-hoc analysis (Levene's or Brown-Forsythe Test), Welsch-Satterthwaite corrections will be applied.

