Study Design and Protocol

An Evaluation of a Milk-Based Nutritional Supplement to Effect a Positive Change in Bone Health in Post-Menopausal Women at Risk of Osteoporosis.

In a novel approach to the timing of nutrient ingestion, the proposed nutrient intervention seeks to modify (reduce) the rate of bone resorption and promote the rate of bone formation to the benefit of bone health in this at risk population.

2. Study design: A block randomised, cross-over design of 24h rates of bone turnover in healthy, post-menopausal women with osteopenia receiving either a milk-based protein supplement (MBPS) or isoenergetic (maltodextran) placebo control (PLACEBO).

3. Procedures:

Subjects: Post-menopausal women with osteopenia as determined by site-specific BMD (DXA) diagnosed and screened by a clinician ([name]) and for dietary intake of calcium and Vit D by a clinical dietitian ([name]).

Subject screening (clinical examination, 1h) and dietary intake of calcium and Vit D (by food frequency questionnaire, 1h) will precede the experimental protocol.

Experimental protocol and data collection: Supplemenary Material contains a Flowchart Subjects will attend for a 2 day overnight residence in the National Altitude Training Centre, Kilmurray Village. This facility is equipped to conduct residential human trials and has on-site individual bedroom accommodation subjects & researchers, a living room with fully equipped kitchen and laboratory to handle human blood samples.

The subjects' programmed protocol is as follows;

- 1. Arrive @ 17:00h with overnight bag;
- 2. Empty bladder and then provide and retain urine samples for the duration of the stay (assisted collection by researchers);
- 3. Consume a standardised evening meal (pre-prepared by the research dietitian) and then relax reading/watching films etc in the living room;
- 4. At 20:00h a research nurse will insert a cannula into a superficial arm vein and a blood draw (5ml) will be taken and processed for later analysis;
- 5. Further blood draws (5ml) will be taken at 22:00h, 2300h, 2400h,0100h and 0200h and the cannula withdrawn;
- 6. At 22:00h consume *either* maltodetran control (**PLACEBO**) (day 1) OR supplement (**MBPM**)(day 2) or *vice versa*;
- 7. Retire to bedroom;
- 8. Consume a standardised breakfast and lunch (pre-prepared by the research dietitian) whilst living in and around the University grounds (i.e. in close proximity to ensure 24h urine collection is complete);

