- 9. Repeat from 2 above to end of 2nd day.

Total blood draw over 48h is $14 \times 5ml = 70ml$

[figure not shown]
- All formulations to be supplied food grade and product tested by Dairygold Coopertaive Society, Mitchelstown, Ireland.
- 4. Analytical methods:
- i. In total 224 (16 subjects * 7 samples * 2 d) blood samples will be collected. Separated aliquots will be frozen @ -80C and batch analysed for CTX (biomarker of resorption), P1NP (biomarker of formation). In total 32 (16 subjects * 2 d) 24h urine samples will be collected. Aliquots will be frozen @ -80C and batch analysed for uPYD, uDPD (biomarkers of resorption) normalised to urinary creatinine.

Ethical approval number: 2017_06_03_EHS

Date of Approval 26th June 2017

- ii. The I.O.F. recommended serum marker for bone resorption is CTX and formation P1NP. The magnitude and time course of the acute response (0-4h) change in bone turnover following ingestion of the MBPM vs. PLACEBO will be analysed by repeated measures ANOVA of the serum biomarkers of resorption and formation.
- iii. The overall influence on the diurnal change in bone turnover is best measured by a global biomarker of bone resorption specific to the type I collagen in bone. This is provided by the measurement of 24h urinary pyridinoline (PYD) and deoxypyridinoline (DPD) excretion normalised for urinary creatinine. Thus, the magnitude of effect of 24h change in bone resorption following ingestion of the MBPM vs. PLACEBO will be analysed by ANOVA(R) of the urinary markers of bone resorption (PYD/creatinine and DPD/creatinine).

Schematic Flow Chart of the Trial

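### The crossover model has no term for night, so any shift between the two nights would cost precision, mainly in the 24h urine comparison

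*SAP*

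**What the plan says.** The SAP states the design as "Study Design: A block randomised, crossover design" in 16 women and gives the model as "MODEL: Mixed model analysis of variance". Its list of independent variables has two entries, TIME (six levels) and TEST PRODUCT (two levels). The items under the model repeat both as within-subject factors, the second as "b. Within-subject factor, TEST PRODUCT (2".

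In the Protocol, section 3 (Procedures), step 6 has each woman take one product at 22:00h on day 1 and the other on day 2, in either order. Step 9 reads "Repeat from 2 above to end of 2nd day". For urine, section 4 (Analytical methods), item i, says "In total 32 (16 subjects * 2 d) 24h urine samples will be collected", which is one value per woman per night. Item ii says that the acute response "will be analysed by repeated measures ANOVA of the serum biomarkers of resorption and formation", and item iii specifies a repeated-measures ANOVA of the urinary markers. No period, night, day, order or sequence term appears in either document.

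**The concern.** With both orders in use, product and night are separable, but only if the model contains night. If levels on night 2 differ from night 1 by a constant amount, women given placebo first show the product effect plus that amount, and women given the supplement first show it minus that amount. A model without night treats this systematic spread as random disagreement between women about the product effect.

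The nights need not be alike. Night 2 follows a night in the facility with blood draws to 02:00h (Protocol section 3, step 5), whereas nothing is specified for the hours before the 17:00h arrival on day 1. With 16 women and no stated power calculation, precision that can be recovered for almost nothing is worth recovering. The 24h comparison is one of the two parts of the null hypothesis, and its urine outcome has no TIME contrast within a night from which a shift could cancel.

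**Working it through.** **From the documents:** 16 women, two products, two consecutive nights, either order; 16 x 2 = 32 urine samples, which agrees with the Protocol. No alpha, power, effect size or SD is given, so there is no power figure to reproduce.

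**Assumed:** 8:8 sequences; two-sided alpha 0.05; SD of the within-woman product difference (within a sequence) set to 1; a product effect of 0.753, chosen because it gives 80% power with PERIOD in the model; night shift *s* (night 2 minus night 1) of 0 to 1 SD.

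**Model for the difference (supplement minus placebo):** effect + *s* if placebo came first, effect - *s* if the supplement came first.

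- Without PERIOD: expected error variance = 1 + *s*² x 16/15, on 15 df.
- With PERIOD: error variance = 1, on 14 df.
- Ratio of CI widths (without / with) = square root of that variance x 2.131/2.145, the two t quantiles.

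For *s* = 0.5, the variance is 1 + 0.25 x 16/15 = 1.27 and the CI ratio is 1.125 x 0.994 = 1.12. Power and type I error are from simulation:

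| Shift (SD) | Error variance | CI ratio | Power without PERIOD | Power with | Type I error without |
|---|---|---|---|---|---|
| 0 | 1.00 | 0.99 | 80.4% | 80% | 5% |
| 0.25 | 1.07 | 1.03 | 78-79% | 80% | 4.3% |
| 0.5 | 1.27 | 1.12 | 73% | 80% | 3.0% |
| 0.75 | 1.60 | 1.26 | 63% | 80% | 1.5% |
| 1.0 | 2.07 | 1.43 | 50% | 80% | 0.6% |

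Type I error with PERIOD stays at about 5% throughout.

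**Unequal sequences.** Without PERIOD the bias is *s* x (n1 - n2)/(n1 + n2). For *s* = 0.5 this is 0.5 x 1/15 = 0.03 SD at 8:7 and 0.5 x 2/14 = 0.07 SD at 8:6. Type I error stays below 5% in both cases. With PERIOD the bias is zero.

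**Blood.** For the product main effect the same algebra applies to the night means, and simulation over five times (0-4h) gave the same power figures. In one simulated 16 x 2 x 6 data set, adding a constant shift left the product mean square at 7.77 and raised the subject x product mean square from 2.63 to 9.06, so F fell from 2.96 to 0.86. The PRODUCT x TIME F was 0.235 both times.

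The blood power figures cover 0-4h only. The SAP's TIME factor also has a 24h level, and 24h after the night-1 product at 22:00h is the night-2 22:00h draw. If one sample serves both, the nights share an observation and the clean between-night error no longer holds.

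**A shift that varies over time** does reach PRODUCT x TIME. With five times, four independent contrasts, the product effect in one of them and about 80% power with PERIOD x TIME, a 0.5 SD night difference in all four contrasts lowers power without that term to about 66-68%. A difference of 0.5 or 1.0 SD in one contrast gives about 77-78% or 67%.

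**The case against.** The strongest reply is that the harm depends on a shift that nobody has shown. Facility, clock times and standardised meals repeat from one night to the next, which argues against a large one. At 0.25 SD the loss is negligible, and with no shift PERIOD costs a little power. All of this stands, and it limits the weight of the point. It does not remove it, because at 8:8 the cost is 0.4 points of power against a gain of about 7 to 30 points for shifts of 0.5 to 1.0 SD.

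It is also fair that the acute question concerns the size and time course of the 0-4h change, which is mainly PRODUCT x TIME. A reader might infer that the acute blood result is compromised. A constant shift cancels there, so the firm consequence is for urine.

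A reader might also infer that the product effect is biased, or that false positives rise. At equal sequences neither happens: the estimate is unbiased and the test conservative. Nor do the documents support calling 16 women too few on this ground, since they state no effect size or power target.

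Could the words *mixed model* cover order implicitly? A between-subject sequence factor would do so through its interaction with product, but the listed factors are both within-subject and sequence is not among them. On the other hand, the named repeated-measures ANOVA and sphericity corrections indicate that PRODUCT is already tested against subject x product. There is no ground for saying that the SAP tests it on a pooled residual.

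**Conclusion.** The point holds as one of efficiency. The stated model omits night from a two-night AB/BA crossover, so a constant night shift would widen the interval for the 24h urine comparison and for the blood product main effect. The size rests on assumed shifts, 8:8 sequences and an assumed 0.753 SD effect: negligible at 0.25 SD, about 7 points of power at 0.5 SD, about 30 points at 1.0 SD. Bias arises only if the sequences become unequal, and it is small in the cases examined. Validity is not threatened.

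**What to change.** Amend the SAP to include PERIOD (night) as a fixed effect.

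- **Urine:** PERIOD and PRODUCT, with subject as a random effect.
- **Blood:** PERIOD, PRODUCT, TIME and PRODUCT x TIME within the repeated-measures ANOVA, with PRODUCT still tested against between-night, within-subject error. If fitted as a mixed model, use random effects for subject and for subject x night. Consider PERIOD x TIME as well, since a night difference that changes over the sampling times inflates the PRODUCT x TIME error. State how the 24h level is handled, given that after the night-1 product it coincides with the night-2 22:00h draw.
- **Reporting:** the product effect with its 95% CI.

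The cost is wording only: order is known from randomisation and no new data are needed. The product test goes from 15 to 14 error df at 8:8. If there is no shift, power falls from 80.4% to 80.0% at 8:8, from 77.4% to 76.7% at 8:7 and from 74.1% to 72.7% at 8:6. PERIOD does not address carry-over from the first night to the second.

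### SAP item c corrects by Bonferroni without fixing the set of comparisons: name the product-versus-placebo comparisons for each marker and test them with Holm

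*SAP*

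**What the plan says.** SAP, Statistical Analysis, sets a mixed-model ANOVA with TIME at six levels (0, 1, 2, 3, 4 and 24h) and TEST PRODUCT at two, applied to three dependent variables: CTX, the blood formation marker and urine DPD/creatinine. Item c then reads, in full, "Bonferroni corrected post-hoc comparisons". It does not say:

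- which comparisons are meant;
- whether the correction spans times, markers or both;
- what alpha is;
- whether a significant interaction is needed first.

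The null hypothesis is more specific. Against placebo, the supplement "will not affect the temporal acute (0-4h) and diurnal (24h) rates of bone turnover". Protocol 4.ii likewise sets the serum question as "The magnitude and time course of the acute response (0-4h) change in bone turnover", supplement against placebo.

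The sampling text bears on which comparisons can exist:

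- **Blood.** Protocol 3, steps 4 and 5, list one draw at 20:00h and then "Further blood draws (5ml) will be taken at 22:00h, 2300h, 2400h,0100h and 0200h", which makes six per evening. Protocol 4.i counts seven per day: "In total 224 (16 subjects * 7 samples * 2 d) blood samples will be collected". Step 9 says "Repeat from 2 above to end of 2nd day".
- **Urine.** Protocol 4.i counts 32 collections, one per woman per product. Protocol 4.iii analyses both PYD and DPD over creatinine. The SAP lists only DPD.

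**The concern.** Bonferroni divides alpha by the number of tests. If that number is not written down, the per-test threshold is undefined, and the same p-value can be called significant or not depending on which family is declared. Someone who has seen the results could choose the family, even in good faith.

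A generic all-pairs procedure would also spend most of the alpha on questions the hypothesis does not ask, such as placebo at 1h against supplement at 3h. With 16 women there is little power to spare. And where several times truly differ, single-step Bonferroni gives up power that a step-down version keeps at the same error rate and with no further assumption.

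**Working it through.** **The plan's own counts.** 16 × 7 × 2 = 224 samples and 14 × 5 ml = 70 ml both reproduce. The listed clock times give 6 × 2 = 12 draws per woman, so 16 × 12 = 192 samples and 12 × 5 = 60 ml. Urine: 16 × 2 = 32. The sample size of 16 cannot be reproduced, because no alpha, power, effect size or SD is given.

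**Possible families per marker, from the 6 × 2 layout.** There are 12 cells, so C(12,2) = 66 pairs:

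- 6 compare products at the same time;
- 2 × C(6,2) = 30 compare times within one product;
- 66 − 6 − 30 = 30 differ in both.

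Only the six same-time product pairs address the hypothesis. The 0h pair is taken at the hour of ingestion and is a reference, not an acute effect. That leaves 1, 2, 3 and 4h, plus 24h if it can be formed.

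**Can a 24h blood pair be formed?** The first product's 24h point falls at 22:00h on the second evening, which is also the second product's 0h draw. The second product's 24h point would fall at 22:00h on the third evening. No listed step contains that draw, but six listed draws plus one at 24h would give the seven per day that are counted. The family is therefore four or five, depending on how the schedule is reconciled.

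**Power at one time.** Assumptions, none from the documents: two-sided 0.05, normal paired differences, effect in SDs of the paired difference. The formula is a paired t-test with n = 16, df = 15 and noncentrality effect × √16, at threshold 0.05/m.

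| m | threshold | 0.6 SD | 0.8 SD | 1.0 SD |
|---|---|---|---|---|
| 1 | 0.0500 | 61.2% | 84.8% | 96.2% |
| 4 | 0.0125 | 36.5% | 64.3% | 85.9% |
| 5 | 0.0100 | 33.1% | 60.6% | 83.5% |
| 6 | 0.0083 | 30.5% | 57.6% | 81.3% |
| 66 | 0.00076 | 8.2% | 22.8% | 45.8% |

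At 0.8 SD, four rather than six gains 64.3 − 57.6 = 6.7 points; five rather than six gains 60.6 − 57.6 = 3.0.

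**Holm against Bonferroni on the same four comparisons.** Holm compares the ordered p-values with 0.05/4, 0.05/3, 0.05/2 and 0.05, stopping at the first failure. Simulated with 40,000 trials per setting at 0.8 SD, Bonferroni gives 64–65% power per true difference throughout. Holm gives:

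- 73–78% if all four times differ (correlation between times 0 to 0.8);
- about 71% if three differ (correlation 0.5);
- 67–68% if two differ (correlation 0 to 0.8);
- about 65% if one differs, which is no gain.

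The chance of at least one rejection is the same under both methods. Holm's gain lies in how many times can be claimed.

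**Error across markers.** At 5% per marker, with independent markers: two serum markers 1 − 0.95² = 9.75%; three variables 1 − 0.95³ = 14.3%; four, if both urine ratios are kept, 1 − 0.95⁴ = 18.5%.

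**Use of the 0h sample.** Let r be the correlation between the product difference at 0h and the later one (not in the documents). Subtracting 0h changes a same-time effect of 0.8 SD to 0.8/√(2(1 − r)). Power at 0.05/4:

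| r | ignore 0h | change from 0h | 0h difference as covariate |
|---|---|---|---|
| 0 | 64% | 32% | 60% |
| 0.5 | 64% | 64% | 75% |
| 0.7 | 64% | 88% | 91% |

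**Carryover.** The second product's 0h draw comes 24h after the first product, and no washout is described. Suppose the supplement leaves an effect c at that draw which is gone by the later draws. Women given the supplement first then have their placebo change shifted by −c, and the others are unaffected. With equal sequences, the change-from-0h product difference is biased by c/2. If c persists equally through the later draws, it cancels from the change but shifts the same-time difference by −c/2.

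**The case against.** The strongest reply is that Bonferroni is a valid method, that naming the contrasts is a wording matter, and that Holm is a preference. Much of this stands. Item c contains no statistical error, and Holm gains nothing if only one time differs. Holm also gives up simple simultaneous confidence intervals. What remains is that an unstated divisor is not a pre-specified rule. On any given family Holm never rejects less than Bonferroni and assumes nothing more.

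A reader might infer three stronger things that the documents do not support.

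- **That the plan will correct over all 66 pairs.** It does not say so; 66 is only the upper limit of what item c permits.
- **That no 24h blood comparison is possible.** The count of seven per day fits an extra 24h draw, and the flow chart is not shown. The protocol's "Total blood draw over 48h is" does not settle it either: 22:00h on the third evening is 53h after the 17:00h arrival, but exactly 48h after the first ingestion.
- **That every comparison should be made as change from 0h, with a gain in power.** Protocol 4.ii does speak of change over 0-4h, but the gain depends on an unstated correlation. With r between 0 and 0.2, Holm over four changes from 0h has 32–50% power, below the 57–58% of Bonferroni over six same-time pairs. The covariate does better than subtraction at each value of r tabulated.

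**Conclusion.** The concern holds as a gap in pre-specification with a cheap and better alternative, not as an invalid analysis. The threshold per marker is open between 0.05/4 and 0.05/66, a factor of 66/4 = 16.5. Measured on one analysis scale at 0.8 SD, limiting the family to four product comparisons rather than six is worth about 7 points of power per time, or about 3 if 24h makes it five. Holm adds 0 to 13 points on the four.

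These sizes rest on two-sided 0.05, 16 complete pairs, normally distributed differences and an assumed effect. None of these except the 16 is in the documents, and they do not cover the rank transformation in SAP item i. The need to name the family does not depend on them. This should be changed, but the trial does not fail without it.

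**What to change.** First reconcile two things: the blood schedule (six listed draws per evening, seven counted per day, 24h as a TIME level) and the urine markers (PYD and DPD in the protocol, DPD alone in the SAP). Then replace item c with wording such as:

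> For each blood marker, the post-hoc family is MBPS versus placebo at 1, 2, 3 and 4h (plus 24h if a separate 24h sample exists for both products), tested with Holm's step-down at two-sided 5% per marker. Within-product time comparisons are descriptive. Each urine marker, with one 24h value per product, is a single product comparison.

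Also state:

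- that the 5% is per marker, with the across-marker totals above, or how it is shared across markers;
- whether a significant interaction is required first (Holm controls the error without it);
- that the comparisons include a period term, which removes a shift between evenings but not carryover;
- whether and how 0h is used. Change from 0h should not be required. The 0h product difference as a covariate is the more efficient option in the figures above. Any use of 0h should address carryover into the second evening, and say whether ranking under item i comes before or after the adjustment.

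The cost is SAP text only, with no more women, samples or assays. The downside is that Holm has no simple simultaneous intervals, so 95% confidence intervals must be labelled unadjusted and may exclude zero where Holm does not reject.

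### The SAP calls its model mixed, but the steps it sets out are classical repeated-measures ANOVA, which drops a woman with any missing modelled draw; neither document says what happens to missing draws.

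*SAP*

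**What the plan says.** The protocol (section 4, Analytical methods, item ii) says the acute 0-4h serum response "will be analysed by repeated measures ANOVA of the serum biomarkers of resorption and formation".

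The SAP (Statistical Analysis) names ANOVA(R). It lists TIME with six levels (0, 1, 2, 3, 4 and 24h) and TEST PRODUCT with two, both as within-subject factors. Item ii tests with Mauchly's W and, on violation, "e correction factors (Green-House Geisser, Huynh-Feld) will be applied". The SAP also has the line "MODEL: Mixed model analysis of variance". It gives no random effects, covariance structure, estimation method or degrees-of-freedom method.

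The sample is "16 post-menopausal women aged 50 to 70y diagnosed with osteopenia". The protocol (section 3, Procedures, steps 4 and 5) lists a draw at 20:00h and five more from 22:00h, ending "2400h,0100h and 0200h and the cannula withdrawn". This is repeated on the second night. Section 4, item i counts seven blood samples per woman per day, 224 in all.

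Neither document mentions missed draws, an incomplete night, imputation or an analysis set.

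**The concern.** Mauchly's test and the epsilon corrections are computed from the covariance matrix of complete within-woman vectors. If the analysis follows those steps, a woman with one empty TIME by PRODUCT cell has no usable vector. She leaves every test of that marker, including those at times where her data are complete. A missed draw does this for both CTX and the formation marker, because they share the sample; an assay failure affects one marker only.

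With 16 women, each exclusion costs precision and can unbalance the two sequences, which weakens the crossover's protection against a difference between nights. If tolerance of a product or of the night causes the loss, keeping only complete women also selects on tolerance. A likelihood-based mixed model keeps the observed draws and is valid under the weaker missing-at-random assumption.

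**Working it through.** **Inputs.** From the SAP: 16 women, 6 TIME levels and 2 products. From the protocol: 7 samples per day by count, 6 draw times by list. Assumed, because the documents give none: the loss rate per draw.

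**The plan's own count.** 16 × 7 × 2 = 224, as stated. The listed draw times give 16 × 6 × 2 = 192.

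**Cells per woman.** The SAP's table has 6 × 2 = 12 cells. The 0-4h data alone give 5 × 2 = 10. The 20:00h draw is not a TIME level, so missing only that draw excludes nobody.

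**One missed modelled draw.** On simulated 16 × 2 × 6 data with one cell deleted, a standard repeated-measures ANOVA routine refused to run until the woman was removed. That left 15 women and 15 × 12 = 180 observations. Error degrees of freedom fell from 75 to 70 for TIME and TIME × PRODUCT, and from 15 to 14 for PRODUCT. A mixed model kept 16 women and 191 of 192 observations.

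**Expected complete women**, 16 × (1 − p)^cells, with independent loss p per draw:

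| p | 12 cells | 10 cells |
|---|---|---|
| 1% | 16 × 0.886 = 14.2 | 16 × 0.904 = 14.5 |
| 2% | 16 × 0.785 = 12.6 | 16 × 0.817 = 13.1 |
| 5% | 16 × 0.540 = 8.6 | 16 × 0.599 = 9.6 |

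With 12 cells, the chance of losing at least one woman is 1 − 0.99^192 = 85.5% at 1% loss and 97.9% at 2%.

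**Clustered loss.** Loss from a failed cannula falls within one woman's night, so for the same overall rate it removes fewer women. Suppose a fraction f of nights lose the cannula before the last draw and single draws are also lost at rate p. On 10 cells the expected number complete is 16 × (1 − f)² × (1 − p)^10:

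- f = 5%, p = 1%: 16 × 0.9025 × 0.904 = 13.1.
- f = 10%, p = 2%: 16 × 0.81 × 0.817 = 10.6.

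**Precision.** The quantity simulated was the product difference in mean 1-4h change from 0h, with 16 women, five times on two nights, woman SD 1, woman-by-night SD 0.4 and residual SD 0.3. With no loss its SD is 0.3 × √(1.25 × 2/16) = 0.119. The excess of the complete-case SD over the mixed-model SD, across simulations of 150 to 4,000 runs, was:

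- 2% loss: 7-13%
- 5% loss: 25-30%
- 5% of nights with cannula failure plus 1% single-draw loss: 7-12%
- 10% of nights plus 2%: 16-22%

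The 150-run figures carry a Monte Carlo error of about 6% on each SD. As a rough check against no loss, √(16/13.1) = 1.11 and √(16/9.6) = 1.29, which agrees with about 10% and 25-30%.

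**What losing women means for detectability.** For a paired comparison at two-sided 5% and 80% power (both assumed), the detectable standardised difference is 0.75 with 16 women, 0.78 with 15, 0.85 with 13 and 1.07 with 9.

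**Sphericity.** Random intercepts for woman and woman-by-night alone impose compound symmetry. With complete data and AR(1) correlation of 0.7-0.9 within a night, the equivalent uncorrected TIME × PRODUCT test had a simulated type I error of 7-8%, against 4-5% with Greenhouse-Geisser. A mixed model without a suitable covariance would therefore remove a safeguard that the SAP now has.

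**The case against.** The strongest reply is the SAP's own model line. A reader might infer that the plan excludes women with missing draws. It does not say so: listwise deletion is nowhere written, and a likelihood-based mixed model would keep those women. That stands. Exclusion follows from the steps listed, not from a stated rule. But every operational step is classical and nothing that defines a mixed model is given, so the text needs changing on either reading.

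A reader might also infer that a blocked cannula or an early stop is to be expected. The documents do not support this. The cannula withdrawal in step 5 is the scheduled removal after the last draw, a research nurse inserts the cannula, and women stay in a residential facility. The 224 is a planned collection total and sets no analysis rule.

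A third inference would be that the TIME (6) analysis has no complete women at all, because no listed draw gives a 24h value after night 2. The documents do not establish this: the count of seven samples leaves room for a further draw, and the flowchart is not available here. What stands is that the passages disagree.

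Finally, the simulations fit a mixed model whose form is correct by construction, which is its best case.

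**Conclusion.** The point holds as an unresolved model specification with no provision for missing draws, and it is worth correcting before analysis. As operationally described, the serum analysis discards all of a woman's data on a marker when one modelled value is missing. If losses are near 1% per draw, the expected cost is one or two women. At 5% independent loss nearly half would go on the SAP's 12 cells (8.6 of 16 left), with a 25-30% larger sampling SD on the 0-4h data. The sizes rest on assumed loss rates and assumed variance components. Independence overstates the number of women lost if losses cluster. If no draw is lost, the missing-data concern has no effect and only the ambiguous model label remains.

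**What to change.** For CTX and the formation marker, state that the mixed model is a linear mixed model:

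- fitted by REML to all observed draws;
- fixed effects TIME, TEST PRODUCT, TIME × TEST PRODUCT and period (night);
- a random woman effect and a pre-specified within-night covariance that does not assume sphericity, for example AR(1) plus a woman-by-night effect;
- Kenward-Roger degrees of freedom.

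Remove the Mauchly and epsilon step from this analysis only because that covariance replaces it; random intercepts alone must not. State that a woman with missed draws stays in with the data she has. Report the epsilon-corrected complete-case ANOVA as a sensitivity analysis. Say how the rank transform in item i would apply to the new model.

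Reconcile the 24h TIME level and the seven samples per day with the six listed draw times, and say which serum sample supplies the 24h value for each product.

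The cost is SAP wording and a different procedure in standard software, with no extra women. Clarifying the 24h value adds no samples to the 224 already planned if it is among them. The downside is small: a covariance structure must be fixed in advance, with only 16 women to estimate it.

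### SAP item iii prescribes an independent-groups variance check and Welch-Satterthwaite correction for post-hoc comparisons that are all within-woman

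*SAP*

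**What the plan says.** The SAP describes "A block randomised, crossover design" in "16 post-menopausal women aged 50 to 70y diagnosed with osteopenia". Its only independent variables are TIME (six levels) and TEST PRODUCT (two levels), and items a and b label both as within-subject. No sequence, period or group factor is listed. The model line reads "MODEL: Mixed model analysis of variance".

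Item c calls for "Bonferroni corrected post-hoc comparisons" without giving their number, their error term or whether they are paired. Item i sends non-normal data to ranks, and item ii covers sphericity for the omnibus test. Item iii begins "Violation to homogeneity of variance for post-hoc analysis", offers Levene's or the Brown-Forsythe test as the check, and ends "Welsch-Satterthwaite corrections will be applied".

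The protocol confirms that the same women supply both arms. Under Procedures (Experimental protocol, step 6) each woman takes one product on one day and the other product on the other day. Section 4.i counts 16 subjects, 7 samples and 2 days, and 16 × 7 × 2 = 224 blood samples, as stated.

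**The concern.** Two kinds of post-hoc comparison are available: product against product at a time point, and one time point against another. Both compare measurements on the same women. Item iii treats them as if the two sets of values came from separate groups. The documents name no between-group comparison to which it could properly apply.

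The stated hypothesis concerns the time course of the acute response (0-4h), and the post-hoc comparisons are what would locate an effect in time. If the check fires and the two sets of values are positively correlated, the standard error is too large and a real difference can be missed. If they are negatively correlated, it is too small. Because item c names no error term and item iii does not choose between its two checks, two analysts could also reach different p-values from the same data.

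**Working it through.** **Inputs from the documents.** n = 16 women; both factors within-subject; no between-subject factor.

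**Assumed, because the documents do not give them.** Within-woman correlation ρ; variance ratio between the two cells; a paired t-test as the default post-hoc test; a trigger level of 0.05; alpha of 0.01 (0.05/5), 0.05/6 (one product comparison at each of six times) or 0.05/15 (all pairs of six times, 6 × 5/2 = 15). The plan has no power figure to reproduce.

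**Step 1: standard errors.** For cells with SDs s1 and s2:

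- Welch: SE² = (s1² + s2²)/n
- Paired: SE² = (s1² + s2² − 2ρ·s1·s2)/n

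The paired form holds whatever s1 and s2 are. In simulation at nominal 0.05 its type I error was 0.049-0.051 at SD ratios of 1 and 2.

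Ratio of Welch SE to paired SE:

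| ρ | Equal SDs: 1/√(1−ρ) | 4:1 variances: √(5/(5−4ρ)) |
|---|---|---|
| 0.5 | 1.41 | 1.29 |
| 0.7 | 1.83 | 1.51 |
| 0.8 | 2.24 | 1.67 |
| 0.9 | 3.16 | 1.89 |

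At 4:1 the Welch degrees of freedom are 15 × (1+4)²/(1+16) = 22.1 against 15 for the paired test. That gain does not make up for the larger standard error.

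**Step 2: power under the conditional rule.** Bivariate-normal pairs, n = 16, 40,000 runs per setting, true difference set for 80% paired power (noncentrality 3.851 at alpha 0.01). Welch is used if Brown-Forsythe is significant at 0.05, otherwise the paired test. Range over ρ = 0.5-0.9:

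| Variance ratio | Trigger fires | Power under item iii |
|---|---|---|
| 1:1 | 2% or less | 78-80% (with 1.5:1) |
| 1.5:1 | 1-6% | 78-80% (with 1:1) |
| 2:1 | 5-15% | 74-77% |
| 4:1 | 58-63% | 40-67% |

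At 4:1 the values for ρ = 0.5, 0.7, 0.8 and 0.9 are 67.5, 55.5, 48.1 and 40.1%. Alpha hardly matters: the 4:1 range is 40-67% at 0.05/6 and 38-66% at 0.05/15. With Levene as the trigger (alpha 0.01) power is 72-75% at 2:1 and 32-66% at 4:1. In the 4:1 runs where Brown-Forsythe fires, Welch has about 53% power at ρ = 0.5 and 14% at ρ = 0.9, against about 76% for the paired test in the same runs.

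**Step 3: type I error at 4:1, nominal 1%.** 0.6-0.7% for ρ = 0.5-0.9, 1.0% at ρ = 0, 1.4% at ρ = −0.3 and 1.75% at ρ = −0.5.

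**Step 4: is 4:1 realistic?** If SD is proportional to the mean, a 4:1 variance ratio needs a two-fold mean difference, which the paired test usually detects easily. Largest losses with Brown-Forsythe, alpha 0.01 unless stated:

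- 1.25-fold, CV 20-40%: about 2 points.
- 1.41-fold (2:1 variances), CV 20-40%: about 6 points (85.3% to 79.4% at CV 40%, ρ = 0.7).
- 2-fold, CV 20-40%: about 2 points.
- 2-fold, CV 50%: about 8-10 points, or 9-12 at alpha 0.05/6.

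With Levene the largest loss at CV 40% or less is 8.9 points (1.41-fold). A two-fold difference with only 80% paired power would need a CV of 60-88%.

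**Step 5: effect of item i.** Lognormal data, CV 30-40%, SD proportional to the mean: Shapiro-Wilk sends 30-48% of runs to ranks, and Brown-Forsythe on the ranks then fires in under 1% of those. This ranks values pooled over the two cells; the SAP does not say how it ranks. With 4:1 variances at about equal means, the overall trigger rate is about 39-45%.

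**The case against.** The strongest reply is that the SAP never calls the post-hoc tests unpaired. It specifies a mixed model, and Satterthwaite degrees of freedom are legitimate for contrasts in such a model or with a pooled error term. Item iii may be loose wording and not an intention to discard the pairing. That possibility stands, but it does not rescue the text. Item iii makes the correction depend on a test of equal variances between cells, which belongs to the two-sample use. Within-subject covariance is already dealt with in item ii. On either reading the item needs rewriting.

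The second reply is that the harm is conditional and mostly small. It needs the independent-groups reading, a trigger that fires, positive correlation and a post-hoc contrast that matters. Nothing in the documents points to a 4:1 variance ratio without a matching mean shift. Under positive correlation the rule is conservative, so it does not inflate false positives. All of this is right, and it limits the severity. It would also be wrong to judge the size from Welch applied unconditionally at equal SDs, where the check fires in 2% of runs or fewer.

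Finally, separate paired t-tests are not the only valid replacement. Mixed-model contrasts with a stated covariance structure and degrees-of-freedom method would also serve.

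**Conclusion.** The point holds, as a minor one. Item iii does not fit the design, and where correlation is positive it has no compensating benefit over paired contrasts. That much follows from the text and the standard-error formulas. How much it costs depends on an independent-groups reading of item iii and on a correlation, variance ratio, alpha, trigger level and default test that the documents do not give. Under the assumptions shown, the loss is a few points or less in most settings. It becomes large only if one condition is far more variable without a matching shift in mean, or if the between-woman CV is very high. The omnibus within-subject ANOVA is not affected.

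**What to change.** Delete item iii and add under item c: *All post-hoc comparisons are paired within woman and Bonferroni-adjusted; each uses its own SD of within-woman differences.*

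If contrasts inside the mixed model were intended, state the covariance structure and that their degrees of freedom are Satterthwaite, and remove the Levene/Brown-Forsythe trigger.

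Either change costs only SAP wording. Data collection, sample size and the omnibus analysis stay as they are.
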